1. DEMQOL
2. GDS-SF
3. ULS
4. NPI-NH

8.0 TIMELINE AND VISIT SCHEDULE

Assessment / Interview / Data to Collect	Screening	Baseline	Intervention Period	Post-Treatment
Informed Consent Form (Legally Authorized Representative or PWD)	X			
Assent (PWD)	X			
Confirm That the PWD Meets Eligibility Criteria	X			
Enrollment (if person meets basic eligibility criteria)	X			
SPMSQ (Baseline)		X		
DEMQOL (Baseline)		X		
GDS-SF (Baseline)		X		
ULS (Baseline)		X		
NPI-NH (Baseline)		X		
MPES (Baseline Database of Existing Means / SD)		X		
MPES (Intervention Period)			X	
Satisfaction / Ease of Use Questions			X	
DEMQOL (Post-Treatment)				X
GDS-SF (Post-Treatment)				X
ULS (Post-Treatment)				X
NPI-NH (Post-Treatment)				
DEMQOL (Post-Treatment)				X
NPI-NH (Post-Treatment)				X

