1.0 STUDY OVERVIEW

Study Title:

SAFE at Home: A Service to Provide Social Engagement to Community-Dwelling Persons with Dementia

The proposed Phase 1 study will involve initial development and evaluation of a new service called Social Activities For Engagement at Home or SAFE at Home (SaH). SaH will enable PWD to participate in videoconference-based group activities with their peers—i.e., other PWD.

The SAFE at Home app will consist of five main components:

- (1) Get to Know You Portal
- (2) Social Engagement Portal
- (3) Peer-to-Peer Interaction Portal (To Be Developed in Future Phase II Study)
- (4) Self-Study Portal (To Be Developed in Future Phase II Study)
- (5) Staff Training Portal
- (6) Scheduling Portal (To Be Developed in Future Phase II Study)

The study will be conducted by two teams over the course of 12 months. The Development Team (DT) will be responsible for providing the overall vision for the app, as well as website / app development, training creation, and content creation. The Experimental Team (ET) will be tasked with all investigatory work on the project.

Participants

A total of 12 PWD living at home are expected to complete the quasi-experiment. We plan to oversample by 25% to accommodate attrition.

Inclusion / Exclusion Criteria

PWD must be at least 65 years old, speak and read conversational English, and be diagnosed with dementia (any type). PWD will be excluded from the study if they show signs of rapid cognitive decline or physical deterioration over the last six months, as evidenced by medical records.

Baseline Period/Measures

During the 4-week baseline period, the ET will collect the following data. PWD Demographics, medications, diagnoses, and type of dementia will be collected via proxy (family member) interview. The following assessments will be administered directly: The Short Portable Mental Status Questionnaire (SPMSQ-T; Roccaforte et al., 1994), the Dementia Quality of Life Scale (DEMQOL; Smith et al., 2005), the Geriatric Depression Scale-Short Form (GDS-SF; Yesavage & Sheikh, 1986; Yesavage et al., 1983), and the UCLA Loneliness Scale (ULS; Wongpakaran et al, 2020). Researchers will interview family members (FMs) using the Neuropsychiatric Inventory-Nursing Home (NPI-NH; Cummings, 1997; Wood et al., 2001). Using the Menorah Park Engagement Scale (MPES; Camp, Skrajner, & Gorzelle, 2015), researchers will observe PWD engagement and affect via videoconference on four days.

Intervention Period/Measures

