- a. This study will use the MPES in this study to examine engagement and affect of PWD. The MPES is an observational scale that measures four types of engagement: Constructive Engagement: motor/verbal behavior exhibited clearly in response to the target activity; Passive Engagement: listening/watching a target activity; Distracted Engagement: motor/verbal behavior exhibited in response to something other than the target activity; and Non-Engagement / Apathy: outward signs/indicators of apathy, such as sleeping, closing one's eyes, and staring into space. The MPES also measures Pleasure, defined as clearly observable smiling or laughing.
- b. For the Phase I study, we will use a large database of participants engaging in activities as the baseline MPES scores. An independent samples t-test will be conducted to examine differences.
 - 0. ~~If a person has not been seen in group activities after three visits and/or if a staff member has told us the person does not attend group activities, we will consider the person a “chronic non-activity attender.”~~
 - 1. ~~We will then target this person in particular in future visits.~~
 - 2. ~~We will ask staff to invite up to three non-attenders per activity.~~
 - 3. ~~If the person attends, we will observe them in the activity.~~
 - 4. ~~If they do not attend, we will go to the person’s room during the session and find out if they are awake or asleep (knock on the door).~~
 - 0. ~~If they are awake, it will be coded as DID OTHER for more than half.~~
 - 1. ~~If they are asleep, it will be coded as SLEPT/CLOSE EYES for more than half.~~
- c. Please note: all MPES observations will be conducted via a HIPAA compliant Google Form. Submitted responses will automatically be sent to a database. As such, there will be no need to save a corresponding PDF file in each participant's digital binder for each MPES observation. To prevent changing of data in the database, there will be a lock on the database preventing changing of data, except by the PI or Experimental Team Leader. Although each MPES observation will not have a corresponding PDF file in the participant's digital binder, a PDF will be generated for each observation for auditing purposes. The PDFs will be placed in a single folder. MPES observations will be spot checked for accuracy by comparing database data to PDF form data.

Intervention Period Data Collection

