PWD will participate in SAFE at Home for two months during the Intervention Period of the Study. A variety of data will be collected during and/or after the session.

1. Ease of Use and Satisfaction Measure

After each session, the PWDs will be asked simple questions related to ease of use and

satisfaction (e.g., Did you find the activity easy to use? Did you enjoy the activity? Would you recommend it to others?)

2. Observations of PWD in SAFE AT HOME Sessions w/ MPES

- a. Researchers will observe PWD's engagement and affect during SAFE AT HOME sessions using the MPES (Camp, Skrajner, & Gorzelle, 2015). The MPES is described above. There are six different types of activities, and each activity type will be used at least six times by each SAFE AT HOME group. Each participant will be observed multiple times during the intervention period, so that averages can be calculated for each type of engagement/affect.

Post-Treatment Assessments

The following measures will be collected again at post-treatment:

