**SAFE at Home: A Service to Provide Social Engagement to
Community-Dwelling Persons With Dementia**

NCT05516147

Statistical Analysis Plan

12/1/23

The SAFE at Home app will be considered successful if persons with dementia exhibit higher levels of positive engagement/affect and lower levels of negative engagement- as measured by the Menorah Park Engagement Scale (MPES)-during the intervention, as compared to known means for standard programming. Multiple observations of participants will be taken during SAFE at Home programming. Then, means will be calculated for each participant for each item (on the MPES) or positive and negative subscale (for the EPWDS). Then, we will conduct a one-sample *t*-test to determine whether there are significant differences between the known means and the means observed during SAFE at Home programming. We will also conduct paired sample *t*-tests to examine whether participants exhibit an improvement in the Dementia-Related Quality of Life Scale (DEMQOL), Geriatric Depression Scale – Short Form (GDS-SF), Neuropsychiatric Inventory – Nursing Home (NPI-NH), and the UCLA Loneliness Scale (ULS).

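### The SAP and protocol name different t-tests for the same MPES comparison, and neither is assured the right standard error

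*Protocol*

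**What the plan says.** The SAP averages repeated MPES observations within each participant: "means will be calculated for each participant for each item". The test it then names is the one-sample t-test, and the stated purpose is to find out "whether there are significant differences between the known means and the means observed during SAFE at Home programming". The comparator is standard programming.

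The protocol (section 7.0, item 7, and section 9.0, Observations of Standard Activities) takes the baseline MPES scores from a large existing database of participants in activities and says: "An independent samples t-test will be conducted to examine differences". The schedule in section 8.0 lists this source as "MPES (Baseline Database of Existing Means / SD". On the intervention side, section 7.0 has each participant observed several times, "so that averages can be calculated for each type of engagement/affect".

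Section 1.0 gives a third version. Participants' own engagement is observed on four baseline days, and success criterion 3 compares the sessions with baseline. The same section gives the sample size: "A total of 12 PWD living at home are expected to complete the quasi-experiment". It adds: "We plan to oversample by 25% to accommodate attrition".

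Neither document gives the number of people or observations in the database, the unit of its SD (person or single observation), the form of the independent-samples test (pooled or unequal variance), an alpha, or how the two tests relate.

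**The concern.** A one-sample t-test takes its reference value as exact. The protocol describes that value as the mean of a sample, with an SD. The SAP's standard error therefore lacks a term, and its interval is too narrow for any finite database.

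The independent-samples test has that term, but its result depends on what is fed in. Each intervention value is an average over several sessions. If the database SD describes single observations, the two SDs are on different scales. A pooled variance would then come almost entirely from the database, whose units far outnumber the 12 participants.

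Criterion 3 is the only success criterion for which the plan names a hypothesis test. Where the SDs differ in this way, the two tests err in opposite directions, and the same data could be significant under the SAP and not under the protocol.

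**Working it through.** The documents state no MPES mean, SD, alpha or power, so there is no plan figure to reproduce.

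**Inputs.** From the protocol: n = 12 completers (section 1.0), and sessions twice weekly for two months, about 16 (section 9.0). Assumed: two-sided 5%; 12 ratings per participant; 10 ratings per database person; within-person ICC 0.3 to 0.7; 25 to 500 database people; independent participants.

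**1. One-sample test.** Take equal person-level SDs, set to 1, and P database people.
- Test SE: √(1/12). True SE: √(1/12 + 1/P). Ratio of true to test SE: q = √(1 + 12/P).
- The statistic divided by q follows t with 11 df, so the true type I error is Pr(|t₁₁| > 2.201/q).

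| P | q | 2.201/q | Type I error |
|---|---|---|---|
| 25 | 1.217 | 1.809 | 9.8% |
| 50 | 1.114 | 1.976 | 7.4% |
| 200 | 1.030 | 2.138 | 5.6% |
| 500 | 1.012 | 2.175 | 5.2% |

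Simulation with the assumed numbers of ratings agrees: 7.3 to 7.7% at 50 people, 5.6 to 6.0% at 200 and about 5% at 500.

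**2. Pooled test with a per-observation SD.** Set the single-observation SD to 1.
- Variance of a participant's mean: ICC + (1 − ICC)/12. Variance of a database person's mean: ICC + (1 − ICC)/10.
- With 50 people there are 500 observations. At ICC 0.3, the participant variance is 0.3 + 0.7/12 = 0.358 and the database-person variance is 0.3 + 0.7/10 = 0.370.
- True SE: √(0.358/12 + 0.370/50) = 0.193.
- Pooled variance: (11 × 0.358 + 499 × 1)/510 = 0.986. Pooled SE: √(0.986 × (1/12 + 1/500)) = 0.290. Ratio: 1.50.
- The same steps give 0.291/0.237 = 1.23 at ICC 0.5 and 0.291/0.274 = 1.06 at ICC 0.7.

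Simulated results with 50 people, for a shift of 0.9 SD of participant means:

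| ICC | Pooled SE / true SE | Pooled type I error | Pooled power | Welch power (person level) |
|---|---|---|---|---|
| 0.3 | 1.50 | 0.4% | 44% | 75% |
| 0.5 | 1.23 | 1.7% | 66% | 75% |
| 0.7 | 1.06 | about 4% | 76 to 77% | 75% |

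A larger database does not remove this error: with 200 people the ratios are 1.62, 1.32 and 1.14. The direction is not universal. With 25 people and ICC 0.7 the ratio is 0.98, so the pooled SE is slightly too small.

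**3. Pooled test with per-person, equal SDs.** The pooled SE equals the true SE, and the simulated type I error is 4.9 to 5.0%.

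**4. Disagreement between the tests.** At the same shift with 50 people, the one-sample test is significant and the pooled per-observation test is not in 35%, 15% and 6% of runs at ICC 0.3, 0.5 and 0.7.

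**5. Welch's test on person-level means.** Type I error is about 5% throughout, given independent participants.

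**The case against.** A reader might infer that both stated tests are wrong. The documents do not support that. No section says that variances are pooled or that the database SD is per observation. The analysis is planned in SPSS, which also prints an unequal-variance line. With equal per-person SDs the independent-samples test is correct. Averaging within participants is also the right unit of analysis.

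The one-sample error may be small too. The protocol calls the database large, and with several hundred independent people the excess over 5% is under one percentage point. The 7 to 10% figures need 50 people or fewer, which is not established. At ICC 0.7 the pooled test loses essentially no power.

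Testing against a fixed benchmark is also a recognised choice in a small Phase 1 study. If the question were whether participants exceed a declared number, the one-sample test would answer it. The protocol, however, calls for a comparison with a database that has an SD, so the two documents do not ask the same question.

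Finally, criterion 3 in section 1.0 states no significance threshold, so it is partly inference that success turns on the p-value.

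These points limit the size of the problem. They do not settle which test applies or what the database figures represent.

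**Conclusion.** The conflict between documents is firm: one comparison, two different tests, and a third comparator in the protocol overview. It is also firm that the SAP's standard error omits the database's sampling error. The size of that omission depends on an unstated number: type I error is about 7.5% with 50 database people, under 6% with 200 and about 5% with 500, assuming 12 participants and equal person-level SDs.

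The problem with the protocol's test is conditional. It arises if the pooled form is used with SDs that differ, most plausibly because the database SD is per observation. The loss of power is then large at ICC 0.3, moderate at 0.5 and negligible at 0.7. These ICCs and rating counts are assumptions.

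The change should be made because the documents do not let a reader tell which case applies. All the error rates, including Welch's, assume independent participants. Correlation from shared group sessions is a separate matter.

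**What to change.** - In protocol sections 7.0 (item 7) and 9.0 and in the SAP, name one test: Welch's unequal-variance t-test, with one mean per participant per MPES item against one mean per database person, N being people. Report the difference with its 95% CI.
- State how many people the database holds and whether its SD is per person or per observation.
- If only a per-observation SD exists, use it with N = people and say that the interval is conservative. With 50 people and ICC 0.3, type I error is then about 2.4% and power about 66%, against 75% with person-level means.
- Bring the own-baseline comparison in section 1.0 into line with the chosen comparator.

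The cost is mostly wording. The interval will be slightly wider than under the one-sample test, and person-level means may have to be retrieved from the database. The change does not address correlation between participants who share sessions.

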9.0 VISIT PROCEDURES

PWD

Screening Procedures

A researcher will confirm that the participant meets the following inclusion/exclusion criteria by interviewing a family member or obtaining medical records for the person:

Inclusion: PWD must be at least 65 years old, speak and read conversational English, and be diagnosed with dementia (any type).

Exclusion: PWD will be excluded from the study if they show signs of rapid cognitive decline or physical deterioration over the last six months, as evidenced by medical records.

Baseline Procedures

Chart Review/Interview with Staff

Researchers will collect the following data from each PWD's chart:

- Demographics (race/ethnicity, education level, marital status, and number of years living in LTC)
- All diagnoses
- Type of dementia
- All meds

Baseline Assessment

A researcher will schedule a time to work with the PWD and conduct a direct interview with him/her to administer the SPMSQ, DEMQOL, GDS-SF, and ULS.

Caregiver Interview

Researchers will interview a caregiver to collect data related to neuropsychiatric symptoms (based upon the NPI-NH) and agitation (based upon the CMAI) exhibited by the PWD. In addition, if needed (i.e., if the PWD was unable to respond to the DEMQOL and/or GDS-SF questions), a researcher will interview the caregiver to administer the proxy version of the DEMQOL and/or GDS-SF.

Observations of Standard Activities

For the Phase I study, we will use a large database of participants engaging in activities as the baseline MPES scores. An independent samples t-test will be conducted to examine differences.

Intervention Period Procedures

PWD will be invited to participate in SAFE at Home sessions via videoconference twice per week for two months. The sessions will be led by a Life Enrichment Professional.

Observations of SAFE AT HOME Sessions

Researchers will observe the PWD taking part in SAFE at Home sessions using the MPES. We will aim to conduct multiple observations for each activity type, so that an average score can be calculated for SAFE AT HOME activity programming. Researchers will follow the standard protocols for using the MPES and be extensively trained on how to properly use these measures.

Treatment Fidelity / Process / Satisfaction Measures

Researchers will complete a Session Observation / Evaluation Form for each scheduled session, even if the session does not actually occur due to the PWD's unavailability or refusal to participate. Data collected on the Session Observation / Evaluation Form is detailed above.

Post-Treatment Procedures

Post-Treatment Assessment

A researcher will schedule a time to work with the PWD and conduct a direct interview with him/her to administer the DEMQOL, GDS-SF, and ULS.

Caregiver Interview

Researchers will interview a caregiver to collect data related to neuropsychiatric symptoms (based upon the NPI-NH) and agitation (based upon the CMAI) exhibited by PWD. In addition, if needed (i.e., if the PWD was unable to respond to the DEMQOL and/or questions), a researcher will interview the caregiver to administer the proxy version of the DEMQOL and/or GDS-SF.

10.0 FOLLOW-UP

This is a low-risk study of a non-pharmacological intervention. As such, follow up is not required. The final point of contact for PWD will be the post-treatment assessment.

11.0 EARLY DISCONTINUATION

Participants are free to withdraw from participation in the study at any time and for any reason. If they do withdraw, we will no longer collect data on the person.

12.0 SAFETY REPORTING

For the purposes of this study, a participant is considered enrolled if they have successfully completed the screening procedure outlined above. The appointed Safety Officer provides safety oversight of the trial.

After being enrolled in the study, participant safety will be monitored regularly by the PI *and reported as needed to the Safety Officer*.

All adverse events that are both serious (SAE) and unexpected (i.e., have not been previously reported for the study's intervention), they should be reported to IRB, NIA PO and to the NIA-appointed Safety Officer (SO), within 48 hours of the study's knowledge of SAE.

The summary of all other SAEs should be reported to NIA Program Officer and to the DSMB (or a Safety Officer) quarterly (or biannually), unless otherwise requested by the DSMB or a Safety Officer.

Reports of death should be submitted to NIA Program Officer and to the Safety Officer within 24 hours of study's knowledge of death. AEs should be reported per IRB policies. They should also be reported to the NIA Program Officer and the SO, at frequency requested by NIA and/or by the SO. At minimum, annual reports are required.

Adverse Event (AE): Any unfavorable and unintended sign, symptom, or disease temporally associated with the use of a medical treatment or procedure, regardless of whether it is considered related to the medical treatment or procedure.

Serious Adverse Event (SAE): Any AE that results in any of the following outcomes:

- Death
- Life-threatening
- Event requiring inpatient hospitalization or prolongation of existing hospitalization
- Persistent or significant disability/incapacity

As this is a minimal risk psychosocial activity intervention, no AEs or SAEs are expected per NIH definitions, as none of the risks of the study will affect medical outcomes or occurrences.

- The PI will review study conduct in real time.
- The PI will review accrual, drop-outs, and protocol deviations *on an annual basis*.
- The PI will review AEs *individually in real-time, and in aggregate on an annual basis*.
- The PI will review serious SAEs *in real-time, and in aggregate on an annual basis*.
- SAEs and specific procedure-associated AEs will be reported to the Heartland IRB *when the yearly IRB report is due, unless the SAE or AE is “possibly related” or “related” to the study procedures.*
 - *If the SAE or AE is “possibly related” or “related” to the study procedures, the SAE or AE will be reported to the IRB within 24 hours of determination of AE/SAE.*
 - If any SAEs occur, the PI will, with the assistance of the IRB, determine if any modifications need to be made to the study protocol and procedures. As this is a minimal risk study, this is highly unlikely.

12.1 Specification of Safety Parameters

As this is a non-medical, short duration trial with no interim measures (pre-post design), there are no lab values or test scores that fill this role. If a participant becomes extremely embarrassed or agitated during an assessment or activity, they will be redirected, and their participation in the programming will stop for that session. If this occurs at a clinical level that then results in an AE, it will be reported to the IRB when the yearly IRB report is due.

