12.4 Severity of Event

AEs will be graded according to the following scale:

Mild: An experience that is transient and requires no special treatment or intervention.

The experience does not generally interfere with usual daily activities. This includes transient laboratory test alterations.

Moderate: An experience that is alleviated with simple therapeutic treatments. The experience impacts usual daily activities. Includes laboratory test alterations indicating injury, but without long-term risk.

Severe: An experience that requires therapeutic intervention. The experience interrupts usual daily activities. If hospitalization (or prolongation of hospitalization) is required for treatment it becomes an SAE.

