12.6 Follow-up for Adverse Events

Expected AEs

Expected AEs associated with the study procedures include:

- Extreme Feelings of Frustration/Embarrassment during the Assessments / Intervention

AE Management

- Only staff with proper experience in working with vulnerable populations will be permitted to take part in primary data collection. This will increase the chances that they know how to reduce such feelings in participants
- All SPs will receive training on how to recognize signs of frustration and embarrassment and what to do in such situations.
- SPs will be instructed that, if such signs are present, the assessment or activity will be discontinued and/or the participant will be given an alternative activity.

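### Sections 12.1 and 12.6 classify extreme embarrassment differently, so whether an episode counts as an adverse event, and how soon the IRB hears of it, depends on the section applied

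*Protocol*

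**What the plan says.** Four statements in section 12 of the protocol bear on the same kind of episode.

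- **AE definition (12.0).** An AE is "Any unfavorable and unintended sign, symptom, or disease temporally associated with the use of a medical treatment or procedure", whatever its cause. The definition has no minimum severity.
- **Expectation (12.0).** The same section states "no AEs or SAEs are expected per NIH definitions, as none of the risks of the study will affect medical outcomes or occurrences".
- **Handling of an episode (12.1).** "If a participant becomes extremely embarrassed or agitated during an assessment or activity, they will be redirected", and participation stops for that session. The next sentence opens with a condition, "If this occurs at a clinical level that then results in an AE", and sends what meets it to the annual IRB report. Neither the clinical level nor what it means for an episode to result in an AE is explained.
- **Expected events (12.6).** Under the words "Expected AEs associated with the study procedures include" there is one entry: "Extreme Feelings of Frustration/Embarrassment during the Assessments / Intervention". No clinical-level condition is attached.

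On timing, 12.0 and 12.3 allow AEs and SAEs to wait for the annual IRB report unless they are related or possibly related to study procedures, in which case the limit is 24 hours. No section says which of these statements takes precedence.

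**The concern.** A study worker who watches a participant become extremely embarrassed and leave the session has two instructions. Under 12.6 the episode is an AE. Under 12.1 the worker may first ask whether it reached a clinical level, and has nothing to judge that by. Two people applying the protocol in good faith could record different things.

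This is the only kind of expected AE that the visible protocol names, so it is where an AE record for this trial is most likely to have entries. If the threshold in 12.1 is applied, a final count of zero could mean that no episodes occurred, or that episodes occurred and none was judged clinical. A reader of the safety report could not tell which. The classification also decides whether the 24-hour reporting rule is ever considered.

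**Working it through.** The plan states no AE rate, AE count or safety sample size, so there is no figure to reproduce. The check compares the sections on one event.

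**Step 1: find the event that the sections share.** Section 12.1 names extreme embarrassment and agitation. Section 12.6 names extreme frustration and embarrassment. The overlap is extreme embarrassment, and the comparison below is confined to it.

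**Step 2: classify one episode.** A participant becomes extremely embarrassed during a session, is stopped for that session, and recovers.

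| Section | Is it an AE? |
|---|---|
| 12.6 | Yes, by listing |
| 12.0 definition | No severity floor, so nothing excludes it on grounds of degree |
| 12.1 | Only if judged to reach an undefined clinical level and to result in an AE; it can be recorded as no AE |

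**Step 3: the effect on the count.** Let k be the number of such episodes and c the number judged to meet the 12.1 condition, with 0 ≤ c ≤ k.

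- Count under 12.6 = k.
- Count under 12.1 = c.
- Difference = k − c, which runs from 0 (every episode judged clinical) to k (none judged clinical).

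The opportunity for episodes can be sized, though their frequency cannot. Section 1.0 expects 12 completers and an 8-week intervention, and section 9.0 plans two sessions a week: 12 × 2 × 8 = 192 person-sessions, plus the assessments. Nothing in the documents converts that into a value of k.

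**Step 4: expectedness.** Section 12.0 says "As this is a minimal risk psychosocial activity intervention, no AEs or SAEs are expected per NIH definitions". Section 12.6 has a list of expected AEs with an entry in it. For AEs both cannot hold. For SAEs there is no conflict, because 12.6 lists no expected SAE.

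**Step 5: reporting time.** Suppose that an episode is accepted as an AE.

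- 12.1: annual IRB report, with no exception for relatedness.
- 12.0 and 12.3: 24 hours if related or possibly related, otherwise annual.
- 12.6: describes the event as associated with study procedures, which makes a finding of at least possible relatedness likely.

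So the same AE can carry two reporting times. Section 12.5 labels its middle category potentially related; I take this to be the same category as possibly related in 12.0 and 12.3.

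**The case against.** The strongest defence is that the sentence in 12.1 is about reporting. It defers to an AE status decided elsewhere and does not say that lesser episodes go unrecorded. Section 12.0 has the PI review AEs individually in real time, and 12.2 has all staff report to the PI and the Experimental Team Lead. This is fair, and it is why the finding is that 12.1 *allows* an episode to go uncounted, not that it requires this. It does not remove the conflict: 12.6 makes the episode itself an AE, whereas 12.1 speaks of an episode that may or may not lead to one.

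Several stronger readings are tempting, and the documents do not support them.

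- **That 12.0 says distress is not an AE.** It speaks only to what is expected. Its reasoning hints that distress falls outside AE reporting, but it does not say so. The AE definition refers to a medical treatment or procedure, so one could argue that it does not reach distress; 12.6 nevertheless calls the event an AE.
- **That the Mild grade in 12.4 contradicts 12.1.** Mild is "An experience that is transient and requires no special treatment or intervention", but 12.4 grades events already classed as AEs and does not define a case. Whether stopping a session counts as an intervention is also open, so the grade of the example episode is not settled.
- **That leaving agitation out of 12.6 is a contradiction.** The list is introduced as inclusive, and an unlisted event can still be an AE. Agitation is also a symptom that the study measures, through the NPI-NH and, in section 9.0, the CMAI.
- **That distress is the only foreseeable risk.** It is the only expected AE in the visible protocol. The consent form, said to list all potential risks, and the separate Data and Safety Monitoring Plan are not available.
- **That the trial's conclusions are affected.** AE counts enter none of the success criteria in section 1.0 and no analysis in the SAP. Any specific AE percentage would be invented.

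**Conclusion.** The point holds for extreme embarrassment. Sections 12.1 and 12.6 give different rules for whether it is an AE, 12.0 and 12.6 disagree on whether AEs are expected, and 12.1 disagrees with 12.0 and 12.3 on reporting time. For k episodes the recorded count can be anything from 0 to k. That range follows from the text alone and rests on no assumed rate.

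A reader might go further and infer that the same events would support opposite safety conclusions. The documents give no figures from which to show that. What is established is that the record for this event is not determined by the protocol.

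This is an inconsistency that should be corrected in a small, minimal-risk study with no safety endpoint. It does not threaten the efficacy analysis. Section 12.2 leaves the assessing and recording of safety parameters to the PI, and the available text describes no independent adjudication of the undefined threshold; the separate monitoring plan might, but cannot be checked.

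**What to change.** 1. Use one case definition for extreme embarrassment throughout section 12, consistent with the AE definition in 12.0 and the list in 12.6. In 12.1, remove the clinical-level condition as a test of AE status.
2. Narrow the sentence in 12.0 so that it no longer says that no AEs are expected. The part about SAEs can stay.
3. State whether agitation is counted in the same way, and how an agitation AE is distinguished from agitation recorded as a symptom on the NPI-NH or CMAI.
4. Reconcile the IRB reporting time in 12.1 with 12.0 and 12.3. Which time applies is for the sponsor and the IRB to settle.

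None of this touches the clinical response to distress, which stays with the sponsor.

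The cost is rewording 12.0 and 12.1, an added statement on agitation, and a few more AE entries. The AE count may look less favourable than under the 12.1 condition. If the reconciled rule keeps the 24-hour limit for related or possibly related events, some episodes may need reports within that time. That workload should be foreseen when the definition is written.
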